12.2. Dose Limiting Toxicities

The DLT assessment period is from the time of first dose of IP and ends upon administration of the first dose of IP on Cycle 2, Day 1 (28-day cycle).

Any treatment-related toxicities that first occurred during the DLT period must be followed for resolution to determine if the event qualifies as a DLT.

A DLT is defined as the occurrence of an adverse event (AE) that is **at least possibly related to the investigational product (IP) or investigational regimen (IR)**, with two exceptions: any grade of vitiligo or alopecia will not qualify as a DLT. AEs that are **at least possibly related to durvalumab- and/or tremelimumab-containing regimens** shall be assessed as DLTs if they meet known toxicity criteria.

13. PHARMACEUTICAL INFORMATION

13.1. Durvalumab and tremelimumab Pharmaceutical Information

13.1.1. Formulation/packaging/storage

Investigational product vials are stored at 2°C to 8°C (36°F to 46°F) and must not be frozen. Investigational product must be kept in original container until use to prevent prolonged light exposure.

Durvalumab

Durvalumab will be supplied by AstraZeneca as a 500 mg vial concentrate for solution for infusion. The solution contains 50 mg/mL durvalumab, 26 mM histidine/histidine hydrochloride, 275 mM trehalose dihydrate, and 0.02% weight/volume (w/v) polysorbate 80; it has a pH of 6.0 and density of 1.054 g/mL. The label-claim volume is 10 mL.

Durvalumab is a sterile, clear to opalescent, colorless to slightly yellow solution, free from visible particles.

Tremelimumab

Tremelimumab will be supplied by AstraZeneca as a 25 mg vial concentrate for solution for infusion. The solution contains 20 mg/mL tremelimumab, 20 mM histidine/histidine hydrochloride, 222 mM trehalose dihydrate, 0.27 mM disodium edetate dihydrate, and 0.02% weight/volume (w/v) polysorbate 80; it has a pH of 5.5 and density of 1.034 g/mL. The label-claim fill volume is 1.25 mL. Tremelimumab is a sterile, clear to opalescent, colorless to slightly yellow solution, free from or practically free from visible particles.

13.1.2. Study drug preparation of durvalumab and tremelimumab

Based on average body WT of 75 kg, 1500 mg Q4W durvalumab (equivalent to 20 mg/kg Q4W) and 300 mg Q4W tremelimumab (equivalent to 4 mg/kg Q4W) is included in the current study.

Preparation of durvalumab doses for administration with an IV bag

The dose of durvalumab for administration must be prepared by the Investigator's or site's designated IP manager using aseptic technique. Please refer to local prescribing information for in-use storage conditions and times.

A dose of 1500 mg (for patients >30 kg in weight) will be administered using an IV bag containing 0.9% (w/v) saline or 5% (w/v) dextrose, with a final durvalumab concentration ranging from 1 to 15 mg/mL and delivered through an IV administration set with a 0.2- or 0.22-µm filter. Add 30 mL (i.e. 1500 mg) of durvalumab to the IV bag. The IV bag size should be selected such that the final concentration is within 1 to 15 mg/mL. Mix the bag by gently inverting to ensure homogeneity of the dose in the bag.

If weight falls to ≤ 30 kg weight-based dosing at 20 mg/kg will be administered using an IV bag size selected such that the final concentration is within 1 to 15 mg/mL.

Durvalumab, whenever possible, should not be prepared at the same time as tremelimumab. This is because the tremelimumab needs to infuse over a 1-hour timeframe and then have a 1-hour observation time period prior to administration of durvalumab, and durvalumab has a 8-hour expiration from the time it is prepared. Therefore, whenever possible, durvalumab should be prepared closer to the end of the post-tremelimumab observation period. Standard infusion time for durvalumab is 1 hour, however if there are interruptions, the total allowed time must not exceed 8 hours at room temperature.

Do not co-administer other drugs through the same infusion line. The IV line will be flushed according to local practices to ensure the full dose is administered. Infusion time does not include

the final flush time. If either preparation time or infusion time exceeds the time limits a new dose must be prepared from new vials. Durvalumab does not contain preservatives, and any unused portion must be discarded.

Preparation of tremelimumab doses for administration with an IV bag

The dose of tremelimumab for administration must be prepared by the Investigator's or site's designated IP manager using aseptic technique. Total time from needle puncture of the tremelimumab vial to the start of administration must not exceed:

- A total of 24 hours at 2°C to 8°C (36°F to 46°F) of which 4 hours of those 24 can be at room temperature.

A dose of 300 mg will be administered using an IV bag containing 0.9% (w/v) saline or 5% (w/v) dextrose, with a final tremelimumab concentration ranging from 0.10 to 10 mg/mL and delivered through an IV administration set with a 0.2- or 0.22-µm filter. Add 15 mL (i.e. 300 mg) of tremelimumab to the IV bag. The IV bag size should be selected such that the final concentration is within 0.10 to 10 mg/mL. Mix the bag by gently inverting to ensure homogeneity of the dose in the bag.

Standard infusion time is 1 hour, however if there are interruptions, the total allowed time must not exceed 8 hours at room temperature.

Do not co-administer other drugs through the same infusion line. The IV line will be flushed according to local practices to ensure the full dose is administered. Infusion time does not include the final flush time. If either preparation time or infusion time exceeds the time limits a new dose must be prepared from new vials. Tremelimumab does not contain preservatives, and any unused portion must be discarded.

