2. SCHEMA

3. STUDY CALENDAR

Milestone	Screening	I/O		Post I/O Eval ^l	LR Therapy ^m	Transplant ⁿ	Post-op	Long Term Follow-up
Timing		D1	Q4W	28 days post I/O	28 days post I/O minimum	72 days post I/O minimum	Q7 days for 30 days	Q3 mo for 1 st yr then q6 mo up to 5 yrs
Window	-28 days		+/- 3 days	+/- 3 days			+/- 1 day	+/- 4 weeks
Durvalumab ^a		X	X					
Tremelimumab ^b		X						
LR Therapy ^c					X			
Transplant						X		
Consent ^d	X							
Demographics	X							
Medical Hx	X						X ^t	
Con Meds	X							
Physical Exam ^e	X	X	X	X			X ^t	
Vital Signs	X	X	X	X		X		
Height	X							
Weight	X	X	X	X		X		
Child-Pugh	X							
ECOG PS	X	X	X	X	X			
AE/SAEs		X	X	X	X			
CBC w/diff	X	X	X	X	X	X	X	X
CMP	X	X	X	X	X	X	X	X
TSH, amylase, lipase ^f	X		X	X				
INR	X		X	X	X	X	X	
AFP	X			X	X	X		X
βhCG ^g	X							
CT Chest ^h	X			X				
MRI Liver ⁱ	X			X				X ^o
Bone scan (if clinically indicated)	X							
Tumor Assessments ^r	X			X				
Survival Data ^q					X	X	X	X
Rejection Data							X	X ^p
Correlative Blood collection ^j	X ^j			X ^j		X ^j	X ^j	
Stool collection ^k	X							
Tissue collection ^l						X ^l		

I/O: Immunotherapy; LR: Locoregional; CBC: Complete blood count; CMP: Comprehensive metabolic panel (sodium, potassium, chloride, bicarbonate, urea, creatinine, calcium, protein, albumin, AST, ALT, alkaline phosphatase, bilirubin)

a. Up to 5 treatments

b. Tremelimumab is only administered one time on Day 1 of the first cycle – only 1 dose for the entire study. It is not given on the first day of every subsequent cycle.

- c. Per treating physician discretion – TACE, SIRT, etc.
- d. Every effort should be made to minimize the time between consent and starting treatment
- e. Physical exam will be directed toward key symptoms, signs, and safety evaluations, per treating physician's discretion
- f. If TSH is abnormal, then free T3 and/or free T4 should be checked
- g. For women of childbearing potential only. Serum pregnancy test performed within 7 days prior to the first dose of trial treatment. A urine test may be considered if serum test is not appropriate.
- h. With or without contrast, per treating physician discretion
- i. With contrast
- j. Correlative blood samples may be collected with other SOC labs include the following. See Correlative section #9 for more information and the Laboratory Manual.
 - Two 10 mL EDTA tubes which must be collected after eligibility is confirmed but prior to I/O..
 - Two 10 mL EDTA tubes collected at the post I/O evaluation timepoint.

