6.5.1. Pharmacokinetics/Pharmacodynamics data

Long-term follow up on melanoma patients treated with ipilimumab, an anti-CTLA-4 targeting antibody (dosed every 3 weeks [q3w] for 4 doses and then discontinued), shows that patients responding to ipilimumab derive long-term benefit, with a 3-year OS rate of approximately 22%. Furthermore, the survival curve in this population reached a plateau at 3 years and was maintained through 10 years of follow up (Schadendorf et al 2013).

Data from Study D4190C00006 (Phase I trial in NSCLC patients using the combination of durvalumab and tremelimumab) also show an approximately dose-proportional increase in PK exposure for durvalumab over the dose range of 3 to 20 mg/kg durvalumab Q4W or Q2W. (For further information on PK observations in Study 006, please see the current IB). The observed durvalumab PK data from the combination study were well in line with the predicted monotherapy PK data (5th median and 95th percentiles) for a Q4W regimen. The durvalumab + tremelimumab combination regimen will be administered for 4 doses Q4W followed by durvalumab monotherapy Q4W until disease progression for up to a maximum further 8 doses or unless other specific discontinuation criteria are met.

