10.1. Agent Administration

Treatment will be administered on an outpatient basis. No investigational or commercial agents or therapies other than those described below may be administered with the intent to treat the patient's malignancy.

Regimen Description					
Agent	Premedications ; Precautions	Dose	Route	Schedule	Cycle Length
Durvalumab	None	1500 mg	IV	Q4W	4 weeks
Tremelimumab	None	300 mg	IV	1 dose on day 1 of only the first cycle	
The above for up to 4 months (5 doses durvalumab)					

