10.2. Durvalumab + tremelimumab combination therapy

Tremelimumab 300 mg via IV infusion x 1 dose on day 1 of the first cycle, plus durvalumab 1500 mg via IV infusion Q4W starting on day 1, for up to a maximum of 4 months (5 doses of durvalumab). N.B If a patient's weight falls to 30kg or below (≤ 30 kg), then the patient should receive weight-based dosing equivalent to 20 mg/kg of durvalumab Q4W after consultation between the investigator and study physician, until the weight improves to above 30 kg (>30 kg), at which point the patient should start receiving the fixed dosing of durvalumab 1500 mg Q4W).

Patients will be treated with the immunotherapy combination for up to 4 months. After a minimum 28 day gap following the final durvalumab dose, they will undergo locoregional therapy per institutional standards. Eventually, after a minimum 72-day gap from the end of immunotherapy, they will undergo liver transplant.

Tremelimumab will be administered first over 1 hour; the durvalumab infusion will then be started approximately 1 hour after the end of the tremelimumab infusion to allow for a 1 hour observation

period. Standard infusion time for each is 1 hour, however if there are interruptions, the total allowed time must not exceed 4 hours from the start of infusion at room temperature per infusion.

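### Pharmacy and background text conflicts with the treatment plan on tremelimumab schedule and durvalumab dose count, and the operative sections disagree on the infusion time limit (4 hours or 8)

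*Combined protocol and SAP*

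**What the plan says.** **Tremelimumab schedule.** Section 10.2 specifies "Tremelimumab 300 mg via IV infusion x 1 dose on day 1 of the first cycle", and the regimen table in Section 10.1 has "1 dose on day 1 of only the first cycle". The synopsis agrees, and calendar footnote b is explicit: "only 1 dose for the entire study. It is not given on the first day of every subsequent cycle". Section 13.1.2, which tells pharmacy staff how to prepare the drugs, states "300 mg Q4W tremelimumab (equivalent to 4 mg/kg Q4W) is included in the current study". Section 6.5.1 states that the "combination regimen will be administered for 4 doses Q4W followed by durvalumab monotherapy Q4W until disease progression for up to a maximum further 8 doses".

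**Durvalumab doses.** The synopsis, calendar footnote a and Sections 10.1 and 10.2 all set a ceiling of 5 doses over at most 4 months. The sentence in Section 6.5.1 adds 8 possible further doses to 4.

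**Infusion time limit.** Section 10.2 applies one rule to each drug: a standard infusion of 1 hour and, if interrupted, "the total allowed time must not exceed 4 hours from the start of infusion at room temperature per infusion". Section 13.1.2 says, for durvalumab and again for tremelimumab, "the total allowed time must not exceed 8 hours at room temperature". Section 12.1 also gives 8 hours. Sections 12.1 and 13.1.2 require a fresh preparation once the limit is passed.

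**The concern.** These are instructions for handling and giving investigational drugs, and a reader of one section can reach a different instruction from a reader of another. Section 6.6 names graft rejection by a primed immune system as the main risk, and rejection is a component of the primary endpoint (Section 14.1). Any site that acted on Section 13.1.2 or 6.5.1 would change exposure to the drugs behind that risk. There are three centers, and Section 13.1.3 has drug shipped directly to each, so preparation is local.

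Section 15.17.1 defines overdose as a dose above the one the protocol specifies. While the protocol carries more than one schedule, it is unclear whether a second tremelimumab dose or a sixth durvalumab dose is a reportable overdose.

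The infusion limit matters when an infusion is slowed or interrupted for a reaction, which Section 12.1 allows. At that point staff must know whether the bag may still be used.

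**Working it through.** **Reproducing the plan's own figures.** Section 13.1.2 uses a 75 kg reference weight. Dose divided by weight gives 300 / 75 = 4 mg/kg for tremelimumab and 1,500 / 75 = 20 mg/kg for durvalumab. Both match the stated equivalents, so the conflict is about schedule and not about the size of a single dose.

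**Exposure under each section.** Total = number of doses × dose. Interval from first to last durvalumab dose = 28 × (doses − 1) days.

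| Source | Tremelimumab | Durvalumab | First to last durvalumab dose |
|---|---|---|---|
| Synopsis, calendar, 10.1, 10.2 | 1 × 300 = 300 mg | up to 5 × 1,500 = 7,500 mg | 28 × 4 = 112 days (about 3.7 months) |
| 6.5.1 (4 + up to 8) | 4 × 300 = 1,200 mg | up to 12 × 1,500 = 18,000 mg | 28 × 11 = 308 days (about 10.1 months) |
| 13.1.2, every 4 weeks | no count given; 5 × 300 = 1,500 mg if run with 5 durvalumab doses | no count given | not determinable |

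Two assumptions enter the table. The 6.5.1 row applies this study's 300 mg and 1,500 mg doses, because that section gives only dose counts. The 1,500 mg entry borrows the 5-dose durvalumab ceiling from other sections. The 112 days of the first row fit the 4-month limit; the 308 days of the second do not.

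**Could 6.5.1 be describing another trial?** The same paragraph discusses the Phase Ib lung cancer study. Section 6.4, however, gives that study 7 tremelimumab doses every 4 weeks and then 2 more at 12-week intervals. That does not match 4 doses, and the sentence in 6.5.1 is in the future tense. It reads as a description of the regimen to be given.

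**Infusion limit.** 8 / 4 = 2, a two-fold difference. Take an interrupted infusion that ends 5 hours after it began:

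- Section 10.2 counts from the start of infusion: 5 > 4, so the limit is breached.
- Sections 12.1 and 13.1.2 give no start point for the 8 hours. Counted from the start of infusion, 5 < 8 and the limit is met.
- Section 13.1.2 separately gives durvalumab an 8-hour expiry from preparation. If the 8 hours were counted from preparation, the same infusion would comply only if it began within 8 − 5 = 3 hours of preparation.

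The same infusion can therefore be out of limits under one section and within limits under another.

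**The case against.** The strongest reply is that the sections a site uses to treat a patient do not disagree on dose counts. The synopsis, calendar, 10.1 and 10.2 are consistent. Section 10.5 repeats the 4-month limit, Section 6.5.2 describes a single tremelimumab dose in the HCC pilot study that it cites for the dose, and footnote b expressly excludes repeat tremelimumab. Sections 10 and 11 direct sites to the calendar. The 12-dose figure rests on one background sentence, and the every-4-weeks wording in 13.1.2 sits in a weight-equivalence statement. This stands, and it lowers the risk of repeat dosing. It does not remove the conflict, because 13.1.2 addresses those who prepare the drug and refers to this study.

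It can also be said that the 4-hour and 8-hour limits may run on different clocks. That stands in part: only Section 10.2 states a start. But all three sections frame the rule alike, as a 1-hour infusion with an allowance for interruptions, and none says that it means a different clock.

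A reader might infer several stronger points that the documents do not support:

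- That tremelimumab is specified at five times the single dose. Section 13.1.2 gives no number of doses.
- That sites would hold drug differently. None of the three items concerns criteria for holding a dose.
- That the rejection rate presumes one fixed exposure and one fixed gap before transplant. Durvalumab is given for up to 5 doses with several reasons to stop early, and 72 days is a minimum gap, so both vary by design.

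**Conclusion.** The point holds as an inconsistency in the text that bears on safety. The infusion limit is the firmest part: Section 10.2 conflicts with Sections 12.1 and 13.1.2, all of them working instructions, and the limits differ two-fold. How often this changes a decision depends on the undefined start of the 8-hour clock and on how many infusions are interrupted, which the documents do not say.

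The schedule conflict is real but of moderate practical risk. Total tremelimumab is 300 mg under the treatment sections, 1,200 mg under 6.5.1, and 1,500 mg under 13.1.2 only with an assumed count of 5. The durvalumab ceiling is 5 doses, or 12 under 6.5.1 alone. Nothing in the documents shows that any site followed the divergent text.

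The overdose definition stays ambiguous until the passages agree. The sample size and power statements do not use the number of doses or the infusion time, so they are unaffected.

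**What to change.** Reconcile the synopsis, the calendar and Sections 6.5.1, 10.1, 10.2, 12.1 and 13.1.2 so that each carries the same tremelimumab schedule, the same maximum number of durvalumab doses and the same infusion time limit. State the event from which the limit is counted, and whether it applies to each drug separately. Which schedule, count and limit apply is for the sponsor and the drug supplier to decide; this review takes no position on it.

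Send the reconciled text to the site pharmacies, and check doses and infusions already given against it, including whether any should have been reported under Section 15.17.1.

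The cost is a protocol text correction, a pharmacy notice and a check of dosing records at three centers. No change to the design or the analysis is needed.

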13.1.3. Agent Ordering Temperature Excursions and Agent Accountability

Agent Ordering

UC Health Investigational Drug Services licensure does not allow for the shipping of investigational IP across state lines. All agent shipping will be performed by AstraZeneca directly to each participating site.

When IP is received by the site if IP has not yet been prepared it may be transported to a satellite site following the normal SOPs and policies of the local institution. For example, transport of IP from UCMC to UC Health West Chester would be covered under these institutional policies.

Temperature Excursions

Temperature excursions that occur at site are the sponsors responsibility. The Sponsor is responsible for assessment and determination of suitability for use of any Study Drug where there is evidence of temperature deviations during storage or Study specific labelling.

Agent Accountability

Investigational Drug Services (IDS) Pharmacy at UC will maintain IP accountability which should consist of a record of the receipt, dispensing and final disposition of all agents received using institutional Drug Accountability Record (DARF) or other methods of recording, store

and maintain separate Investigational Agent Accountability Records for each agent, strength, formulation and ordering investigator on this protocol, as well as temperature control records.

Each participating institution must designate an entity to perform the same inventory activities as above: IP receipt, dispensation, and destruction of all IP received as well as temperature control records

13.1.4. Investigator Brochure Availability

The current versions of the IBs will be accessible to site investigators and research staff.

14. STATISTICAL CONSIDERATIONS

14.1. Study Design/Endpoints

The primary endpoint of safety is a binary endpoint, and will be assessed in patients undergoing liver transplant. Safety will be assessed using “treatment failure”, defined as rejection, graft loss, death, or loss to follow up within 30 days of transplant. Historically, 10-20% of patients are expected to experience acute cellular rejection within 30 days of transplant. We propose that an observed proportion of 20% failure will be a clear indicator of safety in this pilot study, whereas an observed proportion of 50% failure will be a clear indicator of failure. Using these guardrails, with at least 20 patients going to transplant, we will have 80.6% power to demonstrate a failure proportion of 20% (4 patients experiencing failure) versus a null of 50% (10 patients experiencing failure), with a one-sided alpha of 0.05. With 25 patients going to transplant, the power will increase to 86% (other parameters being the same).

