6.6. Hepatocellular Carcinoma Background

Hepatocellular carcinoma (HCC) is an aggressive malignancy, developing most often in the setting of cirrhosis of the liver (Sohal et al Current Oncol Rep 2011; Gordan et al JCO 2020). For advanced disease, immunotherapy has now become standard of care – a combination of atezolizumab and bevacizumab has shown the best overall survival outcome so far (Finn et al NEJM 2020).

For earlier stage disease, however, there is no systemic therapy standard. The best treatment for HCC in the setting of cirrhosis is a liver transplant allowing potential cure for both the cancer and cirrhosis. Patients with HCC must meet institutional liver transplant criteria. Nonetheless, 25-35% of patients fail to reach liver transplant because of disease progression while waiting for a transplant (Sinha et al, Hepatology 2019) and approximately 15% experience HCC recurrence after transplant (Mehta et al, Transplantation 2020). Taken together, this constitutes a large subset of this patient population who cannot achieve a cure.

Given the success of immunotherapy in the advanced setting, it is imperative to study this in the pre-transplant setting, to improve the outcomes cited above. The major risk, of course, is graft

rejection by the primed immune system. Therefore, before a larger study may be conducted to assess efficacy of this approach, we will undertake this pilot trial to ensure safety – with the primary outcome focusing on acute cellular rejection of the transplanted liver.

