14.2. Sample Size/Accrual Rate

A total of 30 patients are to be enrolled, to allow at least 20 transplants for adequate primary endpoint analysis.

During immunotherapy, grade 3-5 AEs will be monitored. In the pivotal study of durvalumab and tremelimumab (Kelley et al, Abstract 4508 at ASCO 2020), 16% had Tx related (TR) SAEs, and 11% had discontinuation of treatment due to TR AEs. We will use these guardrails for interim safety analyses at 10 patients. We will pause enrollment and assess safety in detail to determine if the study should continue, in discussion with AstraZeneca if:

- Of the first 10 patients, if ≥ 3 patients have to discontinue immunotherapy due to treatment related AEs and/or;
- Of the first 10, if ≥ 3 patients experience SAEs related to locoregional therapy after immunotherapy and/or;
- Of the first 10, if ≥ 3 patients fail to reach liver transplant due to immunotherapy toxicity and/or;
- Of the first 10 patients, if ≥ 3 deaths are encountered, from enrollment to up to 30 days after transplant.

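### Power at 25 transplants should read 89.1%, not 86%, under the exact test that fits the 80.6% at 20; no test or cut-off is named, so 5 failures of 20 can be read either way

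*Combined protocol and SAP*

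**What the plan says.** Section 14.1, repeated in the synopsis, defines the endpoint and its population: "The primary endpoint of safety is a binary endpoint, and will be assessed in patients undergoing liver transplant". Failure means rejection, graft loss, death or loss to follow-up within 30 days of transplant. The historical benchmark is 10-20% acute cellular rejection over the same period.

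The power statement for at least 20 transplants is "we will have 80.6% power to demonstrate a failure proportion of 20% (4 patients experiencing failure"), set against the null: "versus a null of 50% (10 patients experiencing failure"), "with a one-sided alpha of 0.05". It then says: "With 25 patients going to transplant, the power will increase to 86% (other parameters being the same").

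The favourable decision wording is: "We propose that an observed proportion of 20% failure will be a clear indicator of safety in this pilot study". An observed 50% is described as the matching sign of failure. Neither place names a test, gives a maximum number of failures for success, or says how the criterion changes with the number transplanted.

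On enrolment, Section 14.2 says: "A total of 30 patients are to be enrolled, to allow at least 20 transplants for adequate primary endpoint analysis".

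**The concern.** Two things do not fit together.

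First, the two power figures are presented as one calculation at two sample sizes. The exact test that gives the first does not give the second.

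Second, the power belongs to a hypothesis test, while the decision wording is an observed proportion. A test against 50% with 20 patients has a critical count, and that count is not 4. Because the plan states neither the test nor the count, two analysts could follow the same text and disagree on the primary conclusion at 5 of 20. The number transplanted is not fixed in advance, so the same question arises at a different count for each possible n. It should be settled before the data are seen, since the plan describes this as a pilot to establish safety before a larger study.

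**Working it through.** **Inputs** (Section 14.1 and synopsis): null failure proportion 0.50; alternative 0.20; one-sided alpha 0.05; n = 20 and n = 25. The test is not stated. I assume the exact one-sample binomial test, because it comes within 0.2 points of the plan's figure at n = 20.

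**Formula.** Let X be the number of failures among n transplanted patients. The cut-off r is the largest count with P(X ≤ r | n, 0.5) ≤ 0.05. Power is P(X ≤ r | n, 0.2).

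**Step 1: the figure at 20.** P(X ≤ 5 | 20, 0.5) = 0.0207 and P(X ≤ 6 | 20, 0.5) = 0.0577, so r = 5. Power = P(X ≤ 5 | 20, 0.2) = 0.8042. The plan says 80.6%; this agrees.

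**Step 2: the figure at 25.** P(X ≤ 7 | 25, 0.5) = 0.0216 and P(X ≤ 8 | 25, 0.5) = 0.0539, so r = 7. Power = P(X ≤ 7 | 25, 0.2) = 0.8909. The plan says 86%; the difference is 89.1 − 86 = 3.1 points.

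**Step 3: could another method give both figures?** Power at n = 20 / n = 25, one-sided 0.05:

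| Method | n = 20 | n = 25 |
|---|---|---|
| Stated | 80.6% | 86% |
| Exact binomial | 80.4% | 89.1% |
| Score z | 90.3% | 95.5% |
| Score z, continuity correction | 84.6% | 92.6% |
| Arcsine | 89.1% | 94.2% |
| Exact mid-p | 91.3% | 95.3% |
| Null variance under both hypotheses, continuity correction | 79.2% | 87.6% |
| Logit-scale Wald | 79.8% | 87.0% |

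The last two lie within 2 points of both stated figures, but neither returns 80.6 or 86.

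**Step 4: the observed-20% wording taken as a rule.**
- n = 20, 4 or fewer: power P(X ≤ 4 | 20, 0.2) = 0.6296; actual alpha 0.0059.
- n = 25, 5 or fewer: power P(X ≤ 5 | 25, 0.2) = 0.6167; actual alpha 0.0020.

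**Step 5: where the two readings differ.** At n = 20 they differ only at 5 failures: 0.8042 − 0.6296 = 0.1746, a 17.5% chance at a true 20%. The one-sided p-value there is 0.0207, and the observed proportion is 5/20 = 25%. At n = 25 they differ at 6 and 7 failures: 0.8909 − 0.6167 = 0.2742, a 27.4% chance.

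**Step 6: what success would show.** With 4 of 20, the exact one-sided 95% upper bound is 40%. A true failure rate of 30% passes the 5-or-fewer rule 42% of the time, and a true 35% passes 25% of the time.

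**Step 7: number transplanted (a note only).** Thirty enrolled for 20 transplants allows 10/30 = 33.3% loss. Section 6.6 cites a background figure: "25-35% of patients fail to reach liver transplant because of disease progression while waiting for a transplant". With transplants distributed as Binomial(30, 1 − d), the chance of fewer than 20 is 11%, 27% and 49% for d = 25%, 30% and 35%. Exact power is still 83.7% at 19 and 86.7% at 18 (cut-off 5 in both). It is 75.8% at 17 (cut-off 4). Averaged over the number transplanted, it is 88.7%, 86.3% and 83.6% for the three values of d.

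**The case against.** The strongest reply is that nothing here weakens the trial. The 86% is lower than the true figure, so the plan promises less than it delivers, and correcting it changes no sample size. No test is named, and two crude approximations come near both figures, so the slip may come from the method used. This stands: the numerical error is minor and conservative. It remains an error under the one standard test that fits the 80.6%.

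Four stronger readings are tempting, and the documents do not support them.

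- *That the plan has a 4-of-20 rule with only 63% power.* The 4 and 10 are bracketed counts that translate 20% and 50% at n = 20. The plan never writes 4 or fewer, and its 80.6% corresponds to 5 or fewer. The 63.0% applies only if the observed-20% wording is taken as the rule.
- *That 5 to 9 failures of 20 lead to no conclusion.* With the stated null and alpha, 6 to 9 fail to reject under the exact test. The real ambiguity is at 5.
- *That the plan treats rejection of 50% as a clear sign of safety.* It attaches that description to an observed 20%, and 4 of 20 excludes rates above 40%, which is more than excluding 50%.
- *That 30 enrolled leaves the trial underpowered.* The 25-35% is a background rate for progression on the waiting list, not this trial's attrition assumption, and a shortfall of one or two transplants does not take exact power below 80.4%.

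**Conclusion.** Should be fixed. Under the exact one-sided binomial test the power at 25 transplants is 89.1%, not 86%; the figure at 20 is right (80.4% against 80.6%). The actual alpha is 0.021 and 0.022.

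The more consequential gap is that no test or cut-off is stated and the only favourable decision wording sits one failure below the cut-off that the power implies. At 20 transplants the primary conclusion is therefore open for one result, with a 17.5% chance of occurring if the true failure rate is 20%.

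This rests on the exact test being the intended one, which is inferred from the 80.6%. It does not rest on the transplant yield. That the final n may differ from 20 is only a reason to state the cut-off for every n.

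**What to change.** In the synopsis and Section 14.1:

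1. Name the exact one-sided binomial test of a 50% failure proportion at alpha 0.05.
2. State that the primary conclusion rests on the exact cut-off for the number actually transplanted: the largest r with P(X ≤ r | n, 0.5) ≤ 0.05. Examples are 5 for 18-20 transplants, 6 for 21-22 and 7 for 23-25; the general rule covers any other n. More failures than r means that a proportion below 50% has not been shown.
3. Restate power as 80.4% (n = 20) and 89.1% (n = 25).
4. Word success as a failure proportion shown to be below 50%, and report the exact confidence interval beside the 10-20% benchmark. Keep the observed-20% marker, if wanted, as descriptive.

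If the sponsor instead intends an observed 20% or fewer as the success criterion, say so and restate power as 63.0% (n = 20) and 61.7% (n = 25). That choice is the sponsor's: the exact cut-off would accept 7 of 25 (28%), which is above the 20% marker.

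The cost is a wording change in two places and no extra patients. The downside is a more modest claim.
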